AE = adverse event; CBC = complete blood count; ECG = electrocardiogram; EIA = enzyme immunoassay; FU = follow up; HIV = human immunodeficiency virus; HLA = human leukocyte antigen; ICF = informed consent form; RNA = ribonucleic acid; SAE = serious adverse event; vac = vaccination

❶ pre-dose; ❷ no extra blood required; ❸ pre- and post-dose; ❹ for subjects who consent to mucosal secretion collection; ❺ AEs will be recorded from the signing of the ICF.

¹ Screening visit may be split into multiple days/visits.

² Complete physical exam will be performed at the screening and final visits. At all other visits, an abbreviated, symptom-directed exam will be performed as indicated by the investigator. Weight will be measured at every visit.

³ Within 24-72 hours post-vaccination a member of the site staff will have a (remote) safety follow-up communication with the subject (by e-mail, telephone or visit, according to the subject's preference).

⁴ Baseline mucosal secretion sampling may be done at screening or baseline prior to vaccination. (Note: mucosal secretion procedures for both men and women are optional, and will only be performed on a subset of subjects who provide consent.)

⁵ For female subjects who consent to the cervico-vaginal mucosal sample collection

⁶ Urine pregnancy test performed prior to mucosal secretion procedure, only for females who consent to mucosal secretion collection.

⁷ Microscopic reflex testing in the event of positive urinalysis

⁸ If medical status and physical examination on Day 1 suggests significant changes may have occurred since screening, the clinically relevant screening assessments will be repeated and the Day 1 visit rescheduled, provided that the rescheduled visit is within 28 days of the initial screening assessment. In case a grade 3 or grade 4 laboratory abnormality, or any laboratory abnormality accompanied by clinically relevant signs or symptoms occurs (from the baseline visit onwards), a confirmatory test should be performed within 48 hours after the results have become available. After that, laboratory tests will be repeated weekly until values are resolved or stable.

⁹ Measurement of specific cardiac enzymes (troponin); will also occur at later timepoints if cardiac symptoms warrant

¹⁰ An HIV testing algorithm will be followed (detailed in the Study Procedures Manual)

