At Visit 2a (24-72 hour post-vaccination) a member of the site staff will have a (remote) safety follow-up communication with the subject (by e-mail, telephone or visit, according to the subject's preference). The subject will be brought in for a clinic visit based on this assessment, if deemed necessary by the investigator/sub-investigator or upon request of the subject.

Visit 3 is a clinic visit that will include an abbreviated physical examination (including weight measurement), vital signs, and cardiac risk assessment, recording of any AEs and concomitant medications, and review of the memory aid for 8 days post-vaccination (day of vaccination and the subsequent 7 days).

Visit 4 is a clinic visit that will include an abbreviated physical examination (including weight measurement), vital signs, and cardiac risk assessment, recording of any AEs and concomitant medications, and collection of samples for humoral immunogenicity assay, and for safety laboratory testing (CBC, serum chemistry and urinalysis). Subjects who consent to mucosal secretion collection at this visit ([Section 9.1.9](#)) will undergo additional testing for syphilis, chlamydia, gonorrhea, and trichomonas.

Visit 5 is a clinic visit that will include an abbreviated physical examination (including weight measurement), vital signs, and cardiac risk assessment, recording of any AEs and concomitant medications, and collection of samples for cellular and humoral immunogenicity assay, assessment of Ad26 seropositivity, and for safety laboratory testing (CBC, serum chemistry and urinalysis).

At Visits 3 and 4, in addition to an HIV-risk assessment, counseling related to avoidance of HIV infection will be provided to all subjects.

Visits 6a, 7, and 8 (Days 86-88, and Weeks 14 and 16)

The procedures for Visits 6a, 7, and 8 will be the same as at Visits 2a, 4, and 5, respectively, as detailed above, with the exception that blood samples for cellular and humoral immunogenicity assay will be drawn at both Visits 7 and 8. Additionally at Visit 8 only, a 12-lead ECG will be carried out.

Visits 9a, 10, and 11 (Days 170-172, and Weeks 26 and 28)

The procedures for Visits 9a, 10, and 11 will be the same as at Visits 6a, 7 and 8, respectively, as detailed above. (Note: no ECG at Visit 11.)

Visit 12 (Week 36)

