Subjects will be instructed on how to record daily temperature using a thermometer provided for home use. Subjects should record oral temperature in the evening post-vaccination, and then daily for the next 7 days through the memory aid. Temperature should be measured at approximately the same time each day. If more than one measurement is made on any given day, the highest daily temperature will be used in the CRF. Fever will be recorded by the investigator or his/her designee for temperatures equal to or higher than 38.0 °C.

Subjects will also be instructed on how to note daily symptoms through the memory aid for 8 days post-vaccination (including the day of vaccination) of the following events:

- fatigue
- headache
- myalgia
- arthralgia
- chills
- fever
- nausea
- vomiting
- rashes
- general itching

Clinical Laboratory Tests

Blood samples for serum chemistry and hematology will be collected at times specified in the Time and Event Schedule. The investigator must review the laboratory report, document this review, and record any clinically relevant changes occurring during the study in the AE section of the CRF. The laboratory reports must be filed with the source documents.

In case a grade 3 or grade 4 laboratory abnormality, or any laboratory abnormality accompanied by clinically relevant signs or symptoms occurs (from the baseline visit onwards), a confirmatory test should be performed within 48 hours after the results have become available. After that, laboratory tests will be repeated weekly until values are resolved or stable.

The following tests will be performed by a local laboratory (*parameters only measured at screening):

- **Serum chemistry**

| | |
|-------------------------------|-----------------------------------|
| sodium* | alkaline phosphatase* |
| potassium* | phosphate* |
| chloride* | albumin* |
| calcium* | total protein* |
| magnesium* | bilirubin* |
| bicarbonate* | AST |
| blood urea nitrogen (BUN)* | ALT |
| glucose* | creatinine |
| creatine phosphokinase (CPK)* | troponin |
| | FSH (post-menopausal women only)* |

- **Hematology**

hemoglobin

hematocrit
red blood cell (RBC) count
white blood cell (WBC) count with differential
platelet count

- **Urinalysis** – dipstick for
specific gravity
pH
glucose
protein
blood
ketones

Microscopic reflex testing will be carried out in the event of positive urinalysis tests.

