| Magnesium, serum, low | 1.2 – 1.4 mEq/L 0.60 – 0.70 mmol/L | 0.9 – 1.1 mEq/L 0.45 – 0.59 mmol/L | 0.6 – 0.8 mEq/L 0.30 – 0.44 mmol/L | <0.60 mEq/L <0.30 mmol/L |
| Pancreatic amylase | 1.1 – 1.5 \times ULN | 1.6 – 2.0 \times ULN | 2.1 – 5.0 \times ULN | >5.0 \times ULN |
| Phosphate, serum, low | | | | |
| Adult and Pediatric >14 years | 2.5 mg/dL – <LLN 0.81 mmol/L – <LLN | 2.0 – 2.4 mg/dL 0.65 – 0.80 mmol/L | 1.0 – 1.9 mg/dL 0.32 – 0.64 mmol/L | <1.00 mg/dL <0.32 mmol/L |
| Pediatric 1 year – 14 years | 3.0 – 3.5 mg/dL 0.97 – 1.13 mmol/L | 2.5 – 2.9 mg/dL 0.81 – 0.96 mmol/L | 1.5 – 2.4 mg/dL 0.48 – 0.80 mmol/L | <1.50 mg/dL <0.48 mmol/L |
| Pediatric <1 year | 3.5 – 4.5 mg/dL 1.13 – 1.45 mmol/L | 2.5 – 3.4 mg/dL 0.81 – 1.12 mmol/L | 1.5 – 2.4 mg/dL 0.48 – 0.80 mmol/L | <1.50 mg/dL <0.48 mmol/L |
| Potassium, serum, high | 5.6 – 6.0 mEq/L 5.6 – 6.0 mmol/L | 6.1 – 6.5 mEq/L 6.1 – 6.5 mmol/L | 6.6 – 7.0 mEq/L 6.6 – 7.0 mmol/L | >7.0 mEq/L >7.0 mmol/L |
| Potassium, serum, low | 3.0 – 3.4 mEq/L 3.0 – 3.4 mmol/L | 2.5 – 2.9 mEq/L 2.5 – 2.9 mmol/L | 2.0 – 2.4 mEq/L 2.0 – 2.4 mmol/L | <2.0 mEq/L <2.0 mmol/L |
| Sodium, serum, high | 146 – 150 mEq/L 146 – 150 mmol/L | 151 – 154 mEq/L 151 – 154 mmol/L | 155 – 159 mEq/L 155 – 159 mmol/L | ≥ 160 mEq/L ≥ 160 mmol/L |

| CHEMISTRIES Standard International Units are listed in italics | | | | |
|--|---|--|---|--------------------------------|
| Sodium, serum, low | 130 – 135 mEq/L 130 – 135 mmol/L | 125 – 129 mEq/L 125 – 129 mmol/L | 121 – 124 mEq/L 121 – 124 mmol/L | ≤ 120 mEq/L ≤ 120 mmol/L |
| Triglycerides (fasting) | NA | 500 – 750 mg/dL 5.65 – 8.48 mmol/L | 751 – 1,200 mg/dL 8.49 – 13.56 mmol/L | >1,200 mg/dL >>13.56 mmol/L |
| Uric acid | 7.5 – 10.0 mg/dL 0.45 – 0.59 mmol/L | 10.1 – 12.0 mg/dL 0.60 – 0.71 mmol/L | 12.1 – 15.0 mg/dL 0.72 – 0.89 mmol/L | >15.0 mg/dL >>0.89 mmol/L |

| URINALYSIS Standard International Units are listed in italics | | | | |
|---|---|---|---|--|
| Hematuria (microscopic) | 6 – 10 RBC/HPF | >10 RBC/HPF | Gross, with or without clots OR with RBC casts | Transfusion indicated |
| Proteinuria, random collection | 1 + | 2 – 3 + | 4 + | NA |
| Proteinuria, 24 hour collection | | | | |

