### 5.2.1. **Analysis methodology**

Laboratory data will be analyzed based on the full analysis set. Unless specified otherwise, percentages are calculated versus the number of subjects in the analysis set with non-missing data for the parameter, period (if applicable) and treatment group under evaluation.

Tabulations of the worst graded abnormalities per period following vaccination will be provided. Grade 3 and 4 toxicities developed following vaccination will be listed. Tabulations of the worst emerging abnormalities (below/above) will be performed for tests that have no grading.

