## APPENDIX 1: LABORATORY, VITAL SIGNS AND ECG ABNORMALITY GRADINGS

PARAMETER	LABORATORY a			
	GRADE 1 MILD	GRADE 2 MODERATE	GRADE 3 SEVERE	GRADE 4 POTENTIALLY LIFE-THREATENING
HEMATOLOGY				
Absolute Neutrophil Count (ANC) c	1.000 x 10  – 1.300 x 10  /L	0.750 x 10  – 0.999 x 10  /L	0.500 x 10  – 0.749 x 10  /L	<0.500 x 10  /L
Hemoglobin (Hgb) (HIV NEGATIVE ONLY)	10.0 – 10.9 g/dL or Any decrease b 2.5 – 3.4 g/dL	9.0 – 9.9 g/dL or Any decrease b 3.5 – 4.4 g/dL	7.0 – 8.9 g/dL or Any decrease b ≥ 4.5 g/dL	<7.0 g/dL
Platelets, decreased	100.000 x 10  – 124.999 x 10  /L	50.000 x 10  – 99.999 x 10  /L	25.000 x 10  – 49.999 x 10  /L	<25.000 x 10  /L
WBC, decreased	2.000 x 10  – 2.500 x 10  /L	1.500 x 10  – 1.999 x 10  /L	1.000 x 10  – 1.499 x 10  /L	<1.000 x 10  /L
CHEMISTRIES				
ALT (SGPT)	1.25 – 2.5 x ULN	2.6 – 5.0 x ULN	5.1 – 10.0 x ULN	>10.0 x ULN
AST (SGOT)	1.25 – 2.5 x ULN	2.6 – 5.0 x ULN	5.1 – 10.0 x ULN	>10.0 x ULN
Creatinine	1.1 – 1.3 x ULN	1.4 – 1.8 x ULN	1.9 – 3.4 x ULN	≥ 3.5 x ULN
URINALYSIS				
Hematuria	6-10 RBV/HPF	>10 RBV/HPF	Gross, with or without clots or with RBC casts	Transfusion indicated
Proteinuria, random collection	1+	2-3+	4+	NA

a This list is restricted to the laboratory parameters collected in this study for which a DAIDS grading is available. Only ranges applicable for adults are reported. For a complete list refer to the CTP appendix 1

b The decrease is a decrease from baseline

c If ANC is not available the values will be derived by from the ratio Neutrophils/Leucocytes

VITAL SIGNS AND ECG					
PARAMETER	UNIT	GRADE 1	GRADE 2	GRADE 3	GRADE 4
Temperature b	°C	≥38.0 - ≤38.4	≥38.5 - ≤38.9	≥39.0 - ≤40.0	>40.0
Hypertensionb					
Systolic Blood Pressure	mmHg	≥140 - ≤159	≥160 - ≤179	≥180	NA
Diastolic Blood Pressure	mmHg	≥90 - ≤99	≥100 - ≤109	≥110	NA
Hypotension	mmHg	NA	NA	NA	NA
Pulse rate					
Tachycardia	bpm	≥101-≤115	≥116 - ≤130	>130	NA
Bradycardia	bpm	≥50 - ≤54	≥45 - ≤49	<45	NA
QTc ab	msec	≥450 - ≤ 470 or increase ≤30 from baseline	>470 - ≤ 490 or increase >30 and ≤50 from baseline	>490 or increase >50 from baseline	NA

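### The SAP's non-missing-data denominator makes Grade 1-2 hematuria percentages conditional on a positive urinalysis, because microscopy is only a reflex test

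*SAP*

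**What the plan says.** **Denominator.** SAP Section 5.2.1 sets a default for laboratory tables: "percentages are calculated versus the number of subjects in the analysis set with non-missing data for the parameter", and for the period and treatment group concerned. The default yields to any other specification, but the SAP gives none for urinalysis. The output is a worst-grade table: "Tabulations of the worst graded abnormalities per period following vaccination will be provided".

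**Graded parameter.** SAP Appendix 1 has hematuria under urinalysis. Its footnote states: "This list is restricted to the laboratory parameters collected in this study for which a DAIDS grading is available". Grade 1 is 6-10 cells and Grade 2 more than 10 cells per high-power field. Grade 3 is gross hematuria or red cell casts, and Grade 4 is a transfusion indication. Protocol Attachment 1 uses the same scale and names the parameter as microscopic.

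**When the measurement exists.** Protocol Section 9.3.2 says: "Microscopic reflex testing will be carried out in the event of positive urinalysis tests". Footnote 7 of the Time and Events Schedule repeats it: "Microscopic reflex testing in the event of positive urinalysis".

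**Emergence.** Under SAP Section 5.2 an abnormality is emergent if it is worse than baseline, and always emergent when there is no baseline value.

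**Status of the analysis.** SAP Section 1 says that the Week 96 analysis had already been done and would not be repeated. The long-term extension schedule contains no urinalysis.

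**The concern.** A dipstick cannot supply a count of cells per high-power field. A subject whose urinalysis is negative therefore has no value for the graded hematuria parameter, unless the database assigns one. Under the default rule that subject leaves the denominator, although the subject was tested and was negative. The table would then show the proportion with hematuria among subjects with a positive urinalysis, in a layout that reads as incidence in the arm.

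Safety and tolerability form a primary objective, and readers of a regimen-selection study will compare these tables across groups of 50. SAP Section 2.4 also plans laboratory subgroups by sex, race, region and BMI, which divide an already reduced denominator further.

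The emergence rule is affected too. Eligibility requires negative glucose, protein below 1+, and blood below 1+ in men or below 2+ in women. Most subjects would therefore probably have no microscopy before the first dose, and their later graded results would be called emergent by default and not by comparison.

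**Working it through.** The documents state no hematuria rate, positive-urinalysis rate or inflation factor, so there is no figure of the plan's own to reproduce.

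**Inputs from the documents**
- N = 50 subjects per group (protocol Section 3.1).
- Two urinalysis visits per post-dose period, at 2 and 4 weeks after each dose (protocol Section 9.1.5 and the Time and Events Schedule). This makes eight over the four post-dose periods.
- Microscopy after any positive urinalysis, not only positive blood.

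**Input assumed:** p, the chance that a urinalysis visit is positive, varied from 5% to 50%.

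**Formula.** Let X be the subjects with graded hematuria, m those with at least one microscopy result in the period, N those with a urinalysis, and q = m/N. The rule as written gives X/m, and incidence among subjects tested is X/N. Their ratio is N/m = 1/q.

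If the two visits are independent, q = 1 - (1 - p)². If they are fully correlated, q = p. Over eight independent visits, q = 1 - (1 - p)⁸.

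| Assumed p | q, 2 independent visits | Factor | Factor, fully correlated | Factor, 8 independent visits |
|---|---|---|---|---|
| 5% | 0.098 | 10.3 | 20 | 3.0 |
| 10% | 0.190 | 5.3 | 10 | 1.8 |
| 20% | 0.360 | 2.8 | 5.0 | 1.2 |
| 30% | 0.510 | 2.0 | 3.3 | 1.1 |
| 50% | 0.750 | 1.3 | 2.0 | 1.0 |

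For example, at p = 10%, q = 1 - 0.9² = 0.19 and 1/0.19 = 5.3.

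**Threshold.** A factor of 3 or more needs q of at most 1/3, about 17 of 50 subjects with microscopy. With two independent visits this means p of at most 1 - √(2/3) = 18.4%. With eight it means p of at most 4.9%.

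**What a table would show.** Take two graded cases in a group of 50, so that 2/50 = 4.0%. With m = 35, 25, 17, 10 or 5, the rule as written prints 5.7%, 8.0%, 11.8%, 20.0% or 40.0%.

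**Boundary case.** If the database stores a negative dipstick as a normal hematuria result, then m = N and the factor is 1. Neither document says whether it does.

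**The case against.** Much can be said on the other side.

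- **The size is not in the documents.** A reader might infer that hematuria rates are inflated several-fold as a matter of fact. The documents do not support that. They give no positivity rate and do not say how negative dipsticks are coded. Any positive dipstick field triggers microscopy, and women could enrol with some blood on the dipstick, so q may be large. This objection stands: the direction follows from the text, the size does not.
- **Comparisons between regimens.** A reader might also infer that false contrasts between regimens are likely. Randomization makes q similar across arms on average, and protocol Section 11.5 plans no formal safety testing. Small, unequal denominators add noise, but no likely false contrast has been shown. Conditioning on a positive urinalysis could also partly hide a real group difference in positivity.
- **Troponin.** After screening, troponin measurement "will also occur at later timepoints if cardiac symptoms warrant", so the same criticism is tempting. It does not carry over. Troponin is not in SAP Appendix 1, so no graded table is specified for it there, and absence of symptoms is not a troponin result in the way that a negative dipstick is a urinalysis result.
- **Limited clinical reach.** The safety endpoints in protocol Section 9.3.1 and SAP Section 5 are adverse events and reactogenicity, not laboratory grades. Clinically significant laboratory findings are reported as adverse events, and Grade 3 and 4 toxicities are listed whatever the denominator. Grades 3 and 4 of hematuria do not rest on a cell count alone. This stands, and it confines the problem to Grade 1-2 hematuria percentages. Hematology, chemistry and dipstick proteinuria are unaffected.
- **Emergence.** For a subject with a negative baseline urinalysis, calling a later graded result emergent is also what a proper comparison would give. The default matters mainly where the baseline urinalysis was positive without microscopy or was not done.

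None of this supplies the missing denominator rule or says that a negative urinalysis counts as a non-missing hematuria value.

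**Conclusion.** The concern holds in a limited form. Taken together, the denominator rule, the microscopy scale and the reflex-only testing make the Grade 1-2 hematuria percentage conditional on a positive urinalysis. It overstates incidence by 1/q.

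The size is open. Per post-dose period, with two independent visits, the factor runs from about 10 at 5% per-visit positivity to 1.3 at 50%. It is larger if positivity recurs in the same subjects, and smaller over the whole regimen phase. It is 1 if negative dipsticks are already stored as normal results. These figures rest on an assumed positivity rate and on treating subjects with a negative urinalysis as having no graded hematuria.

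A secondary consequence is that, where baseline microscopy is absent, graded results become emergent by default. That most subjects lack it is an inference from the eligibility limits, not a stated figure.

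**What to change.** Add to SAP Section 5.2.1 that, for hematuria:
- the denominator is all Full Analysis Set subjects with a urinalysis result in the period;
- a negative urinalysis counts as not graded, at baseline as well as afterwards;
- the number with reflex microscopy is shown beside the percentage.

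A positive urinalysis without microscopy should be shown as such and not counted as normal.

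A SAP sentence alone would change no planned output, because the Week 96 analysis will not be rerun and the extension collects no urinalysis. The correction should therefore also be delivered as one supplementary hematuria table, or as a footnote to the existing one that gives both denominators. If negative dipsticks were already stored as normal results, a footnote saying so is enough. The cost is that one extra table or footnote, and no new data are needed.

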### 5.3. Vital Signs and ECG

#### 5.3.1. Definitions

Vital sign and ECG measurements will be performed at the time points indicated in the Time and Events Schedule (see CTP). Following parameters will be summarized:

- Temperature (°C)
- Blood Pressure: systolic/diastolic (mmHg)
- Pulse rate (bpm)
- PR (ms)
- QTc (ms)

For definition of emergent refer to section 5.2.

#### 5.3.2. Analysis methodology

Any clinically relevant vital signs and ECG abnormalities occurring from signing of the ICF onwards must be recorded on the adverse event page of the CRF and are analyzed as AEs. Tabulations of the parameters per period following vaccination will be provided. All findings will be listed by subject and by time point. Tabulations of the worst emerging abnormalities will be performed for parameters if applicable (see grading on Appendix 1).

Listings of all the ECG results and ECG abnormalities reported by the ECG reader will be provided.

Physical examination data will only be listed.

## 6. IMMUNOGENICITY

### 6.1. Analysis specifications

The analysis of immunogenicity will be done on the PPI analysis set (Section 2.3).

### 6.2. Immune Response Parameters

Humoral and cellular immune responses as measured by the following immune assays will be analyzed:

#### Humoral response

- Env ELISA IgG-t gp140
- ELISA IgG 1-4
- TZM-BL
- ADCP gp140
- BAMA
- AD26 VNA

#### Cellular response

- ELISpot
- ICS

### 6.3. Immune Response Analysis

No formal hypothesis on immunogenicity will be tested.

#### Humoral assays

For all the humoral assays the immune response values will be  $\log_{10}$ -transformed before any further handling. The  $\log_{10}$ -transformed values will be used throughout the analysis. In the graphs, original values will be displayed on the  $\log_{10}$  scale.

For each assay and at each time point geometric mean of actual values, geometric mean increases and percentage of responders, all with corresponding 95% CIs will be provided in the tables. The definition of responders is defined in

section 6.4. for each assay. Graphical presentations will be provided displaying dots for the subject values and including the geometric mean and the percentage of responders. If available, baseline values will be summarized pooling the 8 groups and will be displayed on the left of each graph. Week 28 and Week 52 timepoints will be plotted next to each other for each group, a line will link the geometric mean (or the median) of the 2 different time points within the same group.

In the graphs the actual values will be shown and the LLOQ cut-off will be visualized, the values below LLOQ or below LOD will be visualized with the value imputed as described in section 6.3.

Vaccine durability will be shown by linear plots of the GM/median for each group.

Reverse distribution curves of the actual values will be provided for selected assays.

For BAMA the median will be reported instead of the geometric mean. Cumulative number of responses across the IgG/antigen classes will be tabulated.

Magnitude-breadth (MB) plots for the BAMA assay will be provided at each timepoint to explore the magnitude (MFI of IgG3 and of IgG breadth binding antibodies) and breadth (number antigens at a given MFI) of each individual serum sample assayed. MB curves will show, for each possible MFI threshold, the fraction of antigens with MFI greater than this threshold.

The group-specific curve obtained as the average MB across all subjects in that group will be displayed. The AUC-MB is calculated as the average of the MFI over the panel of antigens.

